persistent or significant disability/incapacity, or involve congenital abnormality/birth defects. Unanticipated problems will be monitored and reported to the DSMC. The assessment of adverse events will occur via phone calls at all study contacts that occur after the initiation of treatment (study contacts 2 through 11). Adverse events are events that meet the following criteria: 1) suggest the research places subjects or others at increased risk of harm, 2) are unexpected (in terms of nature, severity or frequency) given the research procedures that are described in the study-related documents, and 3) possibly related to study participation. Any SAE will be queried and reported if it meets the definition of an unanticipated problem. All study-related adverse events will be assessed in a timely manner so that NIH, FDA, and the IRB may be notified, as needed. Adverse event assessment, recording, reporting, and investigation will be accomplished through staff training, structured/standardized assessments of untoward occurrences/events, and regular monitoring by the study team. Also, any adverse event that affects the patient's ability to receive cancer therapy will be reported to his or her oncologic care team as soon as possible. The Lead Researcher and PI has ultimate responsibility for ensuring that SAEs are reported in a timely manner. Additionally, the IRB will receive an annual report of all SAEs and AEs meeting the criteria listed above.

2. **Safety data, untoward events, and efficacy data review.** The study team will continuously monitor adverse event data collected using a standardized prompt in contacts 2-11 in the CET, and any adverse event data that come to light at other times (e.g., if a patient or oncologist reports a health event). The study team will review this information no less often than monthly and the DSMC will review these data at least twice per year.
3. **Safety data collection.** Adverse event data will be collected during phone contacts and the final biochemical verification visit.
4. **Frequency of data collection.** In the CET, safety data will be collected from study contact 2 (approximately 1 week prior to a participant's target quit date) through the final study visit (study contact 11, approximately 6 months after the participant's target quit date).
5. **Who will review the data.** Safety data will be reviewed by the Lead Researcher, study physician, and the DSMC.

PROTOCOL TITLE: Comparative Effectiveness Trial of Tobacco Cessation Treatments among Cancer Patients who Smoke

6. **The frequency of review of cumulative data.** The Lead Researcher and study team will review all adverse event data as they are collected. The study physician will review any adverse events that are unanticipated, severe, and possibly related to study procedures, and all serious adverse events among CET participants, as they occur. The DSMC will review cumulative data no less than twice per year.
7. **Analyzing safety data.** Given the modest sample size in this pilot study, we will focus on effect sizes rather than tests of significance when comparing adverse event rates in the two CET conditions. Any unanticipated or serious adverse events in either condition will be thoroughly assessed and examined.
8. **Conditions that trigger immediate suspension of the research.** The CET will be suspended immediately if data suggest there are unanticipated, severe problems associated with treatment in the CET. The NIH will be notified within 5 days if the PI deems it necessary to suspend the study. In the case of a temporary suspension, the PI will develop a plan for continuation of the study and discuss this plan with NIH in a reasonable time frame.
9. **How the study team will adhere to reportable event reporting requirements.** Any reportable events that are unexpected, immediately life-threatening or severely debilitating, and probably caused by study medication will be reported within 1 business day. If new information about study medication risks that was not previously known to investigators or participants is discovered, investigators will prepare a change of protocol with revised study documents or withdraw affected drugs from the protocol within 14 business days. Likewise, the research team will report to the IRB within 14 business days any of the following: failures to obtain properly informed consent for the CET; dosing errors in medication dispensing; unexpected harms to participants or others that are probably related to the study procedures; noncompliance that could affect participants' rights, welfare, or safety; reportable audit findings; breach of confidentiality; failure to suspend study activities during a participant's known incarceration; and unresolved participant complaints. Breaches of confidentiality of PHI will also be reported to the HIPAA privacy officer.

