3.2 Primary & Exploratory Aims

Primary Aims

Aim 1: To establish the feasibility of the CET protocol and procedures in preparation for a full-scale future trial.

Aim 2: To generate estimates of the size of the comparative effects of intensive, cancer-specific smoking cessation treatment versus a generic, lower-

PROTOCOL TITLE: Comparative Effectiveness Trial of Tobacco Cessation Treatments among Cancer Patients who Smoke

intensity recommended smoking cessation treatment in terms of biochemically confirmed 7-day point prevalence abstinence (no smoking in the past 7 days) 26 weeks after a target quit date.

Exploratory Aims

Aim 3: To estimate differences in CET arms in exploratory outcomes including patient acceptability, completion, adherence, costs, and cost-effectiveness.

Aim 4. To elicit input from patients who have experienced cancer to inform study methods and interventions.

Aim 5. To estimate the extent to which treatment effects on abstinence and exploratory outcomes differ across patient subpopulations based on demographics (age, race, sex, ethnicity, socioeconomic disadvantage); nicotine dependence; and cancer site, stage, and treatment phase.

Aim 4. To explore relations between 1) engagement in tobacco treatment and 2) quitting smoking and health and healthcare utilization outcomes, including cancer outcomes overall, and as a function of environmental exposures and, for those enrolled in the CET, randomly assigned treatment condition.

3.3 Study hypotheses.

The primary hypothesis to be tested for Aim 1 is that at least 12% of eligible adult patients who have cancer and smoke cigarettes and are referred to the tobacco treatment outreach team will initiate an evidence-based form of smoking treatment (either Wisconsin Tobacco Quit Line care or treatment offered in the CET).

The primary hypothesis to be tested for Aim 2 is that more-intensive, cancer-specific smoking cessation treatment will increase the log odds of achieving 7-day abstinence 26 weeks after a target quit date by at least 50% over the comparator condition (predicted odds ratio ≥ 1.50).

Exploratory hypotheses include the following:

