4. Differences in rates of treatment reach, retention, and completion by patient factors (demographics, nicotine dependence, smoking history). (Aim 5).
5. Moderation of treatment effects (high- vs. low-intensity) by patient factors. (Aim 5).

PROTOCOL TITLE: Comparative Effectiveness Trial of Tobacco Cessation Treatments among Cancer Patients who Smoke

6. Health outcomes (e.g., cancer mortality, cancer progression, new cancer diagnoses, treatment side effects).

3.5 Primary safety endpoints.

1. Adverse events, by treatment condition.
2. Serious adverse events, by treatment condition.

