4.3 **Criteria for considering participants “enrolled.”** Individuals will be considered enrolled in the study at the point of randomization to a study arm in the CET. Randomization will occur after oral consent to participate and completion of baseline assessments. People who do not complete oral consent and randomization will not be considered fully enrolled and will be replaced until 50 people are randomized in the CET (25 in each arm).

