We will examine reach of the treatment by computing the proportion of all participants meeting inclusion criteria for proactive tobacco outreach who were referred to WTQL, referred to their PCP, and the proportion who were screened for, eligible for, and enrolled/randomized in the CET. As such, the pool of participants for Aim 1 includes everyone eligible for inclusion on at least 1 CRDS report that guides proactive tobacco treatment outreach. The pool of participants included in Aims 2, 3 and 5 will comprise all participants who were randomized to treatment in the CET. The pool for Aim 4 will include all participants who participated in a qualitative interview.

20.4 Statistical Methods.

Descriptive statistics will be used to characterize smoking treatment reach (the proportion of eligible patients who initiate any smoking cessation treatment, and the proportion who enroll in the CET. These rates will be computed overall, and by patient subpopulation.

Logistic regression will be used to estimate the effects of treatment condition on binary outcome data (e.g., abstinence, side effects), overall and by patient subgroups (i.e., moderation effects). Odds ratios and numbers needed to treat will be computed to estimate treatment effect sizes.

Analyses of variance will be used to examine condition effects on continuous variables such as ratings of treatment satisfaction, burden, and treatment effects on ratings of patient experiences and candidate treatment mediators (e.g., withdrawal). Treatment effect sizes will be computed. Cost-effectiveness will be calculated based on the incremental cost-effectiveness

PROTOCOL TITLE: Comparative Effectiveness Trial of Tobacco Cessation Treatments among Cancer Patients who Smoke

ratio of enhanced treatment versus standard treatment per each additional case of abstinence.

Thematic analysis of qualitative interview will identify themes that emerge in patient interviews in the following areas: cancer experiences, supportive care outreach, tobacco history, and tobacco treatment.

20.5 Planned Interim Analysis.

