No formal inferential interim analyses are planned for this pilot study, but safety data will be examined on an on-going basis to determine if individual participants are at risk or if any treatment element or condition is exerting an iatrogenic effect. If any meaningful evidence of this is detected the DSMC will be consulted along with the IRB to consider study discontinuation or changes. If any danger is deemed likely and significant the study will be immediately suspended.

20.6 Handling of Missing Data. The intent-to-treat principle will be applied to primary analyses. Patients who do not initiate smoking treatment via a UW-CTRI study coordinator will be assumed to not have initiated treatment. In analyses of abstinence, cases who do not report abstinence and provide biochemical evidence of abstinence will be coded as still smoking in primary analyses. This will be supplemented by sensitivity analyses to estimate treatment effects under different assumptions regarding missing data (e.g., if 10%, 20% or 30% of people without verified abstinence are abstinent).

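### The between-arm adverse event comparison has only a logistic odds ratio and number needed to treat to draw on, with no interval and no method for zero counts, so at 25 per arm it can fail for uncommon events

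*Combined protocol and SAP*

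**What the plan says.** All references are to the combined protocol and SAP.

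- Section 3.5 makes adverse events by arm, and "Serious adverse events, by treatment condition", the primary safety endpoints.
- Section 23.1 item 7, on the analysis of safety data, says that "we will focus on effect sizes rather than tests of significance when comparing adverse event rates in the two CET conditions". It then adds a case-level provision: "Any unanticipated or serious adverse events in either condition will be thoroughly assessed and examined".
- Section 20.4 gives the model: "Logistic regression will be used to estimate the effects of treatment condition on binary outcome data (e.g., abstinence, side effects"). It gives the scale as well: "Odds ratios and numbers needed to treat will be computed to estimate treatment effect sizes".
- Section 20.5 plans no formal interim test. It has safety data watched continuously for risk to individuals and for harm caused by a treatment element or arm, and says: "If any meaningful evidence of this is detected the DSMC will be consulted along with the IRB to consider study discontinuation or changes".
- Section 4.3 fixes the size: people who do not complete consent and randomization are "replaced until 50 people are randomized in the CET (25 in each arm").

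No confidence interval, upper bound or rule for empty cells is stated for any safety outcome. The only confidence interval in the document belongs to the earlier primary-care trial described in section 2.4. No expected adverse event rate is given.

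**The concern.** Dropping significance tests is reasonable, but nothing that expresses uncertainty takes their place. Item 7 does not say which effect size it means. Section 20.4 is the only place that defines one for a binary outcome, so an analyst following the plan would fit a logistic model and report an odds ratio and a number needed to treat.

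Two things follow. For uncommon events, one arm will often have a count of zero, and the odds ratio then has no usable value. When the odds ratio can be computed, a bare point estimate from 25 against 25 people does not show how little it rules out. Equal or zero counts may be taken as reassurance, and a modest imbalance as harm from one package. The estimates are also meant to inform a later full-scale trial (section 20.2), and without intervals they say little about safety there.

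**Working it through.** **Inputs.** 25 per arm (section 4.3). Effect measures: odds ratio and number needed to treat (section 20.4). True event risk: not stated, so it is assumed equal in both arms and varied. The plan states no safety precision or power, so there is no figure of its own to reproduce.

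**Step 1: when the odds ratio fails.** With x1 and x2 events, OR = [x1/(25 − x1)] / [x2/(25 − x2)]. It is zero if only x1 = 0, infinite if only x2 = 0, and undefined if both are 0. The number needed to treat is 1/(risk difference), so it is undefined whenever the two counts are equal.

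**Step 2: how often an arm is empty.** For true risk p, P(no events in one arm) = (1 − p)^25, and P(at least one empty arm) = 1 − [1 − (1 − p)^25]².

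| True risk p (assumed) | (1 − p)^25 | At least one empty arm | Both arms empty |
|---|---|---|---|
| 2% | 0.603 | 1 − 0.397² = 84% | 36% |
| 5% | 0.277 | 1 − 0.723² = 48% | 8% |
| 10% | 0.072 | 1 − 0.928² = 14% | 0.5% |
| 20% | 0.004 | 0.8% | about 0 |

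The DSMC's twice-yearly tables will hold fewer people. At an illustrative 12 per arm, the chance of at least one empty arm is 1 − (1 − 0.95^12)² = 79% at 5% risk and 1 − (1 − 0.90^12)² = 49% at 10%.

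**Step 3: what a zero count rules out.** With 0 of 25, the exact upper limit of the two-sided 95% interval is 1 − 0.025^(1/25) = 13.7%. The one-sided 95% bound is 1 − 0.05^(1/25) = 11.3%.

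**Step 4: what an interval would show.** The Newcombe interval is built from the Wilson limits of each arm. For 0 of 25 the Wilson upper limit is 1.96²/(25 + 1.96²) = 3.84/28.84 = 13.3%, so 0 against 0 gives 0 ± 13.3 points. Other cases:

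| Events per arm of 25 | Difference (points) | Newcombe 95% interval (points) |
|---|---|---|
| 3 vs 1 | +8 | −9.4 to +26.3 |
| 5 vs 5 | 0 | −22.1 to +22.1 |
| 7 vs 5 | +8 | −15.5 to +30.5 |
| 10 vs 5 | +20 | −5.3 to +42.2 |

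The 7 vs 5 row has OR = (7/18)/(5/20) = 1.56, yet its interval runs from a clear deficit to a large excess.

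**Step 5: are tests the answer?** No. A two-sided 5% test at this size has 16% power for 10% against 20%, and 33% for 20% against 40%.

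**The case against.** The strongest reply is that this pilot disclaims testing and does not rely on the between-arm estimate for safety. Serious and unanticipated events are assessed one by one. The study physician reviews every serious event as it occurs, the team reviews adverse events at least monthly, and an independent DSMC does so at least twice a year (section 23.1). That stands. A reader might infer that effect sizes are the sole safety input, or that some odds ratio triggers action under section 20.5. The text supports neither: item 7 speaks of a focus, and no passage ties DSMC consultation or suspension to an odds ratio. Case review does not, however, supply the comparison by arm that section 3.5 makes an endpoint.

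A second reply is that rarity cannot be presumed. Serious events include hospitalization, in cancer patients followed for about six months, and section 20.4 names side effects, not serious events. This also stands: at risks of 20% or more the empty-arm problem is negligible. Against it, section 23.1 counts as adverse events only those that are unexpected, possibly related and suggestive of increased risk. Read literally, that makes low counts plausible. Applying the odds ratio of section 20.4 to item 7 is an inference, but no other measure is defined.

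A third, tempting reading is that half or more of trials with equal risk would show a sizeable imbalance. The plan's efficacy benchmark ("predicted odds ratio ≥ 1.50"), taken in either direction, gives 54%, 72%, 73%, 59% and 50% at risks of 2%, 5%, 10%, 20% and 30%. The documents set no such threshold for safety. At 2% risk, 47.9 of the 53.5 points come from tables with one empty arm. Apparent harm in one given arm reaches at most about 37%, and a gap of 12 points or more never reaches half at any risk examined.

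**Conclusion.** The concern holds as a gap in the safety analysis. The plan names an effect measure that can break down for uncommon events and gives no interval, upper bound or zero-count method to go with it. Its size depends on event rates that the plan does not state: the odds ratio has no finite, non-zero value in 84%, 48% and 14% of trials at assumed equal risks of 2%, 5% and 10%, and in under 1% at 20%. Whatever the true rate, an empty arm of 25 leaves risks up to 13.7% open, and equal counts of 5 leave differences of about 22 points either way.

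One might infer that the missing interval produces chance imbalances. It does not: they come from having 25 people per arm and would occur just as often with intervals reported. The interval only keeps them, and zero counts, from being over-read. Nothing here argues for restoring significance tests or shows that participants are left unmonitored.

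**What to change.** Keep the approach without significance tests, and amend section 23.1 item 7 and the side-effect part of section 20.4 as follows for adverse events and serious adverse events:

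1. Report the number of participants with an event and the proportion in each arm, with an exact (Clopper-Pearson) 95% confidence interval.
2. Report the between-arm risk difference with a Newcombe 95% interval (an exact unconditional interval would also serve) in place of the logistic odds ratio.
3. Where an arm has no events, report the upper bound for that arm.
4. State that neither comparable safety nor an excess will be concluded from the point estimate alone.
5. Use the same tables for the DSMC's twice-yearly review.

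The cost is a few sentences and a table format, with no new data and no change to design or monitoring. The drawback is that the report will show wide intervals and will not be able to say that the two packages are equally safe.

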24.0 Economic Burden to Participants

24.1 Costs to participants.

PROTOCOL TITLE: Comparative Effectiveness Trial of Tobacco Cessation Treatments among Cancer Patients who Smoke

The only costs that participants may incur are cell-phone charges for minutes spent on phone calls for Wisconsin Tobacco Quit Line (WTQL) services, qualitative interviews, or CET counseling or assessment calls. Participants may incur co-pays if they elect to receive smoking cessation support from their healthcare team, rather than WTQL or CET treatment.

25.0 Resources Available

Will the research be conducted outside School of Medicine and Public Health or UW Hospitals and Clinics (e.g. the researcher does not have an SMPH research feasibility attestation for this study)?	 YES (complete 25.1)  NO (remove text below, but retain this section)
--	---

25.1 Resources available to conduct the research.

1. **Recruitment.** There are more than 600 living patients with head and neck cancer and more than 800 patients with prostate cancer who use tobacco receiving care at UW-CCC. Given this, it is feasible to recruit 50 patients with cancer who use tobacco in to the CET, even if only head and neck and prostate cancer clinic patients are recruited. To increase the likelihood of recruiting enough people with a history of cancer to achieve the aims of the qualitative interviews (maximum 32), those without a tobacco use history will also be included.
2. **Timeline.** We anticipate completing recruitment within 2.5 years and all data collection within 3 years.
3. **Facilities.** We have sufficient private office space, secure and HIPAA-compliant computing infrastructure, computer workstations, and telephone equipment needed to conduct the proactive tobacco treatment outreach and the CET counseling sessions proposed. We also have locked medication storage areas and space and equipment needed to prepare participant mailings, including medication mailings, and to conduct quality assurance checks on all such mailings. We also have private exam rooms for collecting CO samples and a specially equipped private bathroom for collecting and cotinine-testing urine samples. We have locked cabinet space to store saliva samples in need of testing.
4. **Medical or psychological resources.** A study physician ([name]) and psychologist ([name].) will be available to follow-up with participants who experience

PROTOCOL TITLE: Comparative Effectiveness Trial of Tobacco Cessation Treatments among Cancer Patients who Smoke

adverse events of a medical or psychological nature, respectively.

5. **Process to ensure that all persons assisting with the research are adequately informed throughout the study.** All persons assisting in the research will be informed about the protocol during the informed consent process. The oral consent process will be supplemented by written information regarding the CET. Study personnel who obtain informed consent from participants will be trained to mastery of the protocol before consenting any participants. They will be guided through the oral consent process by a thoroughly tested REDCap database that will prompt each step in the consent process, and document completion of each step (with timestamping and change logging). Thorough quality assurance processes will ensure that consent processes are followed as per protocol.

26.0 Multi-Site Research

Not applicable.

28.0 Appendices

Not applicable.
